C.4.1.2. Exclusion Criteria. Subjects will not meet criteria for Schizotypal Personality Disorder (SPD). SPD is excluded to avoid a possible confound from the restricted affect that characterizes SPD. BPD subjects will not meet DSM-5 criteria for past or present bipolar I disorder, schizophrenia, schizoaffective disorder, substance dependence, organic mental syndromes, head trauma, CNS neurological disease, or seizure disorder. Subjects currently meeting DSM-5 criteria for PTSD will be excluded, unless they are in remission or not currently experiencing symptoms. Subjects currently meeting criteria for major depressive disorder will also be excluded (except as described above). However, since depression is commonly associated with BPD (Koenigsberg et al., 1999), too stringent a depression exclusion criteria would yield a clinically atypical BPD sample. For this reason, BPD patients with Axis I depressive disorders other than major depression and those with a past history of major depression, will not be excluded. Suicidal subjects will not be excluded, unless referral to a higher level of care is deemed clinically necessary by the evaluating clinician. Subjects must not have met criteria for a substance use disorder for 6 months prior to entry into the study. All subjects must be free of significant medical illness. They may not have a pacemaker, surgical clips, any metallic implants, or shrapnel fragments that would contraindicate MRI scanning. Pregnant women will be excluded.

C.4.2. Sample Size, Recruitment and Assessment

C.4.2.1 Sample Size. R61 Phase: (see Power Analysis C.4.5.1). 49 BPD subjects will be recruited each for the training and control groups to acquire 39 subjects in each group allowing for a 20% loss for drop out and fMRI movement artifact. R33 Phase: 65 BPD subjects will be recruited each for the training and control groups to obtain 51 subjects per group, allowing for 20% loss.

C.4.2.2 Recruitment:
Subjects will be recruited
by newspaper, radio,
and social media
advertisements and by
referral from the
psychiatry outpatient
department at Mount
Sinai Medical Center, the
Center for the Intensive
Treatment of Personality
Disorders at Mount Sinai
West, and the Bronx VA
Medical Center. We are
confident that we can
meet recruitment goals
for both R61 and R33 as
our Mood and
Personality Disorders
Research Program at
Mount Sinai, which has
been engaged in
neurobiological research
studies of BPD for over

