30 years, has extensive
experience in recruiting
borderline personality
disorder patients for
research. Recently we
have augmented our
recruitment strategy by

	Table	9 1 − A	ssessr	nent M	easures		
	R61			R33			
Assessment	Baseline	Week 2	Week 4	Week 6	Baseline	Termination	Follow- up 1 & 4 months.
SCID-5	X				X		
SIDP	Х				Х		
Medical Hx. & Exam	Х				Х		
Blood Count	Х				Х		
Metabolic & Electrolyte Panel	Х				Х		
TSH, T4, Serology	Х				Х		
Routine Urinalysis	Х				Х		
Urine Drug Screen	Х	X	Х	Х	Х	Х	
Affective Lability Scale (ALS)	Х	Х	Х	Х	Х	Х	Х
Difficulty in Emotion Regulation Scale (DERS)	Х	Х	Х	Х	Х	Х	Х
Dissociative Experiences Scale (DES)	х	Х	Х	Х	х	Х	Х
Beck Depression Rating Scale (BDS)	Х	Х	Х	Х	Х	Х	Х
Columbia Suicide Severity Rating Scale (C-SSRS)	х	Х	Х	Х	Х	Х	Х
Speilberger State- Trait Anxiety Inventory (STAI)	Х	Х	Х	Х	Х	Х	Х
Zanarini Rating Scale for BPD (ZAN- BPD)	Х	Х	Х	Х	Х	Х	Х
Emotion Regulation Questionnaire (ERQ)	х	Х	Х	Х	Х	Х	Х
Perceived Stress Scale (PSS)	Х	Х	Х	Х	Х	Х	Х
Shipley IQ Scale	Х				Х		
Crowne_Marlowe Social Desirability Scale (CMSDS)	Х				X		
Life Events Check- List (LEC-5)	Х	Х	Х	Х	Х	Х	Х
Childhood Trauma Questionnaire (CTQ)	Х				Х		

including additional clinical sites and by engaging an experienced research recruitment company, Bump Digital Marketing (Toronto, Ontario), to develop targeted website ads and a recruitment landing page for our studies. (See **2.5 Recruitment and Retention Plan** for detailed recruitment strategy.)

C.4.2.3. Assessments All subjects receive the diagnostic, medical, self-report assessments and ratings indicated in Table 1. Assessors will be blind to training assignment. Research diagnoses (DSM-5) are made by means of semi-structured interviews, the SADS and SID-P, administered by experienced interviewers (masters or doctoral level clinical psychologists). We have achieved an interrater reliability kappa of .81 for diagnosing BPD.

C.4.2.4. Sex as a biological variable. Based on prior experience we expect to recruit equal numbers of males and females. We will examine the effect of gender upon all findings.

C.4.3 Procedures for Individual Subjects

C.4.3.1 Timeline of Procedures. For both R61 and R33 Phases: Following consent, subjects will be seen for an initial session for baseline clinical interviews and self-report

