instruments (Table 1). Subjects will receive a medical evaluation (see Table 1) and will be randomized (1:1) to CRD training or CD control conditions using a randomization scheme in random blocks of 2, 4 and 6. An online, electronic randomization system will be implemented by the study statistician. The medical evaluation will take place at the Clinical Research Unit (CRU) ([name]). This will include routine blood tests (complete blood count, metabolic and electrolyte panel, thyroid function tests, and a routine urinalysis. The urine drug screen will be administered in our office ([name]) on the day of your Medical Evaluation. On a separate day, subjects will carry out the baseline imaging task (see C.2.6). For R61 Phase: Within about 2 weeks of baseline scan, subjects will begin the manualized CRDtraining or control CD training, which will continue for 6 weeks. At 2-, 4- and 6- weeks, subjects will receive an fMRI scan similar to the baseline scan (different image sets will be employed for each scan, counterbalanced for sequence among scans across subjects) and the assessment measures as indicated in Table 1. For R33 Phase: The procedures will be as in the R61 phase except that training will last for 6 weeks. Following the last session, subjects will receive the termination assessments, including fMRI, as indicated in Table 1. Subjects will return approximately 1- and 4- months after their last session for follow-up (see Table 1).

C.4.3.2 Regulation-Training Procedures, Adherence Assessment and Refinement of the Treatment Manuals for both R61 and R33 Phases

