C.5.1 R61 Phase. Analyses for Aims R61-2a and R61-2b are described in image analysis (C.6.4, below). Aim R61-2c: Data will be checked for normality and appropriate transformations will be applied to normalize them. Data analysis will primarily use linear mixed models, incorporating fixed effects for Training Group (CRD and ES), Session, and Trial Type (Look Neutral, Look Negative, and Regulate Negative), and their interactions, as well as a random effect consisting of an intercept for each participant. We will examine additional models that incorporate and estimate random-effects slope variance across participants on the time effect (i.e., Session). Outcome variables will be repeated measures in self-reported negative affect and reappraisal success (defined as the Look Negative minus Regulate Negative behavioral valence rating at each Session). Although we do not anticipate large differences in

baseline characteristics between the groups, given that the trial is randomized, we will include variables that are strongly unbalanced at baseline (p< 0.01) as covariates in our models.

C.5.2 R33 Phase. Aim R33-1: The primary outcome measure is the Zanarini total score (ZTS;[57]). We compare the change in ZTS from baseline to end of treatment (EOT) between groups by mixed effect models with group, time and their interaction as fixed effects. A similar analysis will be carried out for the additional outcome measures specified in C.3.3. (Table 1), using the Holm's procedure for correction for multiple comparisons. Aim R33-2: The analysis will be as for R61 Aims R61-2 a,b and c. Aim R33-3: The analysis is described in imaging analysis section C.6.3. Aim R33-4: As above, we will use linear mixed models to examine change in ZTS as the outcome variable. Bonferroni corrections will be applied for multiple clinical outcome measures. P-values throughout will be 0.05, two tailed. All analyses will be conducted according to the intent-to-treat principle for both the R61 and the R33 phase. As a sensitivity analysis we will also consider models that adjust for the number of sessions actually received. Missing data will be assumed as MAR. Under this assumption, a mixed model approach that uses all available information will yield reasonable estimates of the effect sizes.

C.6. Image Acquisition and Analysis

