C.6.4 Second-Level Analysis of Group Differences in Treatment Effects. Randomeffects GLM will use two-sample t-tests to compare the neural effects of reappraisal-bydistancing (CRD) and control training. The 3 contrast maps (weeks 2, 4, 6) for each participant in the R61 phase and the EOT versus baseline contrast map for each participant in the R33 phase will be entered as dependent variables in separate GLM in which gender, age, education level, and pre-treatment ALS score will serve as covariates. The speculative purpose of the R61/R33 mechanism justifies setting the alpha level at a relatively liberal value of p<0.05 and a cluster threshold of 50 contiguous voxels. The hypothesized effects of treatment would be supported by findings of significant reductions in PINES activation for emotion regulation in the CRD training compared to the CD control training condition at either weeks 2, 4, or 6 or at EOT. The decision to proceed to the R33 phase is based on finding a statistically significant difference in reduction in PINES activation between the CRD and control conditions. EOT versus baseline contrast maps for all participants in the R33 phase will be entered into a GLM that will use multiple regression to test for differential changes in activation in the regions of interest associated with improvement on clinical outcome variables for distancing training compared to the control condition. The 3 regressors will include: (1) % change in clinical outcome variable; (2) dichotomous treatment type variable; and (3) an interaction term (i.e., product), which identifies activation change related to differential response to the two treatments. The regressors will be centered on zero.

C.7. Power Analyses:

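### The R33 primary model does not adjust for baseline ZTS; a common-baseline model would usually be more precise at almost no cost

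*Combined protocol and SAP*

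**What the plan says.** Section C.5.2 gives the R33 primary analysis: "We compare the change in ZTS from baseline to end of treatment (EOT) between groups by mixed effect models". The model is specified "with group, time and their interaction as fixed effects". No baseline covariate and no common-baseline constraint is stated. The section assumes data missing at random and says that "a mixed model approach that uses all available information will yield reasonable estimates of the effect sizes".

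Other sections mention covariates, but none names baseline ZTS for this model:

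- C.5.1 (R61 behavioural analysis) will include "variables that are strongly unbalanced at baseline (p< 0.01) as covariates in our models".
- C.6.4 (imaging models) says that "gender, age, education level, and pre-treatment ALS score will serve as covariates".
- C.4.1.1 makes education available as a covariate, C.4.2.4 says gender effects will be examined, and C.8 enters concurrent treatment if the entry criteria are relaxed.

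Table 1 schedules the ZAN-BPD at R33 baseline, termination and follow-up. C.4.3.1 places the baseline self-report instruments at the initial session and mentions randomisation after that. On numbers, C.4.2.1 states: "65 BPD subjects will be recruited each for the training and control groups to obtain 51 subjects per group, allowing for 20% loss". C.7 justifies the 51 with an effect size of 0.56, power 0.80 and two-sided alpha 0.05.

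**The concern.** With two visits, a model containing group, time and their interaction has a separate mean for each arm at each visit. With complete data its interaction estimate is simply the difference between arms in mean change. Baseline ZTS enters only as a response. If one arm happens to start higher, the whole of that difference is subtracted from the end-of-treatment (EOT) comparison, although only part of it is expected to persist.

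Because baseline ZTS is listed before randomisation, the two arms share one expected baseline mean by design. A model that uses this fact is, in large samples, never less precise than the planned one and is usually more precise. This is the R33 primary comparison, sized at 80% power with no stated reserve beyond the loss allowance.

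**Working it through.** **Reproducing the plan's figure.** Inputs from C.7: d = 0.56, power 0.80, two-sided alpha 0.05.

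- Normal approximation: 2 × ((1.960 + 0.842)/0.56)² = 50.06, so 51 per group.
- Noncentral t at 51 per group: power 0.7997 (52 would be needed to reach 0.80).
- Loss allowance: 51/0.8 = 63.75, or 64; 52/0.8 = 65. The stated 65 is consistent.

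**Assumed inputs.** The documents give neither r, the baseline–EOT correlation of ZTS, nor k = SD(baseline)/SD(EOT). I take r = 0.3, 0.5, 0.7 and k = 0.8, 1, 1.2, and set SD(EOT) = 1.

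**Complete data.** Per participant:

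- Planned contrast: 1 + k² − 2rk = (1 − r²) + (k − r)².
- Baseline-adjusted contrast: 1 − r².
- Share of variance removed: (k − r)²/(1 + k² − 2rk).

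At k = 1 this equals (1 − r)/2, which is 35%, 25% and 15%. A mixed model with the planned fixed effects, fitted to one simulated data set, returned the same estimate and essentially the same standard error as the difference in mean change.

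**The plan's numbers.** With n = 65 baselines and m = 51 EOT scores per arm, and all available data used, the variance per arm is:

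- Planned model: (1 − r²)/m + (k − r)²/n.
- Constrained model: (1 − r²)/m.

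Example, k = 1 and r = 0.5: 0.75/51 = 0.01471 and 0.25/65 = 0.00385. The saving is 0.00385/0.01855 = 20.7%.

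Variance removed by formula, with simulation in brackets (20,000 trials per cell, EOT scores missing at random):

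| k | r = 0.3 | r = 0.5 | r = 0.7 |
|---|---|---|---|
| 0.8 | 17.7% (17.0%) | 8.6% (7.6%) | 1.5% (0.8%) |
| 1.0 | 29.7% (29.0%) | 20.7% (20.4%) | 12.2% (12.6%) |
| 1.2 | 41.1% (40.0%) | 33.9% (32.6%) | 27.8% (27.1%) |

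At k = r the formula gives zero, and the simulated result is a small loss: 1.0% at 0.7 and 0.7% at 0.8. Both estimators were centred on the true value. REML fits with a random intercept (40 data sets, k = 1, r = 0.5) gave mean standard errors of 0.1925 planned and 0.1720 constrained: 1 − (0.1720/0.1925)² = 20% of variance.

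**Power.** If the planned test has exactly its stated 0.80, the constrained model has about 0.92, 0.88 and 0.85 at k = 1, and 0.87, 0.83 and 0.81 at k = 0.8, for r = 0.3, 0.5 and 0.7.

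**The case against.** The strongest reply is that nothing is broken. The planned model is standard and unbiased, and the sample size follows from its inputs. The benefit rests on two quantities absent from the documents and could be negligible: 1.5% at k = 0.8 and r = 0.7, and nothing at k = r. All of this stands, and it limits the point to an efficiency gain of unknown size. The simulated savings are also slightly below the formula in eight of the nine cells.

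A second objection is technical and matters for the remedy. The only random structure the plan describes is a participant intercept (C.5.1). If the group term were dropped while that structure was kept, precision could fall when the two SDs differ: by roughly 1–2% of variance at k = 0.8, r = 0.7 and 5–7% at k = r = 0.8. The unstructured covariance is therefore an essential part of the change.

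Third, the imbalance rule in C.5.1 refers to the models generally and might be read as reaching R33. Even so, under randomisation a p < 0.01 trigger would bring in baseline ZTS in only about 1% of trials.

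Fourth, the ALS covariate in C.6.4 is not the baseline of the imaging outcome, so it is no exact precedent. It shows only that the team already adjusts for a pre-treatment clinical score elsewhere.

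**Conclusion.** The point holds as a missed precision gain in the R33 primary analysis. At the planned 65 and 51 per arm, the variance removed ranges from 1.5% to 41% over the assumed grid. It vanishes at k = r, where adjustment costs about 1%. The result rests on baseline ZTS being taken before randomisation, on the missing-at-random assumption the plan already makes, and on the assumed r and k.

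No power shortfall is claimed. C.7 does not say which SD standardises 0.56, so the true power of the planned contrast cannot be fixed, and the power figures above hold only if it is exactly 0.80.

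**What to change.** For Aim R33-1, prespecify a longitudinal mixed model for ZTS with these features:

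- time and group-by-time terms, with no group main effect, so that the baseline means are equal across arms;
- an unstructured visit covariance, so that baseline and EOT variances may differ;
- all available scores included, in keeping with the plan's intent-to-treat and missing-at-random statements.

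An ANCOVA of EOT ZTS on arm and baseline ZTS is an alternative, but it omits participants without an EOT score.

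State that baseline ZTS is used whatever the observed imbalance, so that the p < 0.01 rule does not govern it. Apply the same form to each secondary scale with its own baseline. Settle the wording before R33 outcomes are examined by arm.

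The cost is SAP text and at most one degree of freedom, with no new data or visits.

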- C.3.2. Choice of Regions of Interest for Imaging Analyses. We will assess negative reactivity by examining activation of the Picture Induced Negative Emotion Signature (PINES) network. We selected this network because its activation has been demonstrated to be specific to and monotonically proportional to subjective reactions to the negative picture stimuli we are employing. Moreover, it has been shown to outperform the three ROI's, the amygdala, insula and ACC, and seven whole brain networks, including the salience, default and somatomotor networks, commonly associated with negative affect [33]. Although PINES network activation is our primary neural outcome measure, we will also separately examine activity in each of the above specific ROI's and in the salience, default and somatosensory networks. Although not primary outcome measures, we will also examine the effect of training upon the top-down control regions implicated in cognitive reappraisal that have been highlighted in the metaanalysis by Buhle et. al. [48]: the dorsolateral prefrontal cortex (dIPFC), the ventrolateral PFC (vIPFC), the posterior dorsomedial PFC (dmPFC) and the posterior parietal cortex (PPC). C.3.3 Outcome Measures. R61: The primary outcome measure will be change in PINES network activity. Other outcome measures will be change in activity in the top-down control regions described above and in behavioral valence ratings of the image stimuli during reappraisal. R33: The primary outcome measure will be change in BPD symptomatology (total score in the Zanarini Rating Scale for Borderline Personality, self-report (ZAN-BPD, [57])). Secondary outcome measures will be the ZAN BPD sector scores, Affective Lability Scale total (ALS, [58], Perceived Stress Scale (PSS; [59]), Difficulty in Emotion Regulation Scale Scores (DERS; [41]), Beck Depression Scale score (BDI) and State-Trait Anxiety Scale Score (STAXI). C.3.4 Rationale for Eye Gaze and Pupilometry Measures. Eye gaze direction will be assessed in both R61 and R33 phases to determine whether changes in BOLD activity during regulate conditions are associated with diversion of gaze [60] away from emotionally salient portions of the pictures. Change in pupil diameter (regulate-look) will be recorded during each scan, as an index of cognitive effort [61].

C.4.0 Specific Design and Methods

C.4.1 Subject Inclusion and Exclusion Criteria for R61 and R 33 Phases

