R61 Phase: The primary outcome measures are decreases from baseline in PINES network activity in the REGULATE (vs. LOOK) conditions in CRD training vs. the CD condition at the 2-, 4-, and 6-week treatment doses. A significant effect at any dose will meet milestone criteria. In our previous work (see C. 1.3.3 above), we obtained a strong effect size of d = 0.73 for 5 days of training. We will, however, power the current study at a more moderate power of d = $\underline{.65}$ to increase our detection sensitivity. We can achieve this at α = 0.05 (\underline{two} — tailed), power = 0.80 with an n = $\underline{39}$ per group (G-Power 3.1). **R33 Phase:** The primary outcome measure for the R33 is the effect of CRD-training upon BPD relevant symptoms, assessed by the Zanarini Rating Scale (see C.4.2.3). A meta-analysis of randomized controlled clinical trials of psychotherapy for BPD reported an effect size of 0.56 for seven stand-alone trials employing BPD-relevant outcomes [65]. Powering to detect an effect size of 0. $\underline{56}$ with a power of 0.80 at \underline{two} -tailed α = 0.05 requires 51 subjects per group.

C.8 Potential Study Complications and Alternative Outcomes

Recruitment Shortfall: We will closely monitor the rate of subject recruitment. If the rate at the 3- or 6-month time points, extrapolated, suggests that the recruitment goals will not be met, we will implement the measures described in section 2.5 (Recruitment and Retention Plan), including, modifying exclusion criteria to allow entry of subjects currently on psychotropic medication and /or in psychotherapy, provided that dose or session frequency has not changed in the prior 2 months. Treatment will be recorded and entered as a covariate in analyses. R61: Alternative Outcomes: It is possible that, contrary to our hypothesis, CRD-, will not be superior to CD-training in reducing PINES activity. While such a finding would not meet milestone criteria, this observation would motivate future research to further explore the active features of CD (as well as nonspecific factors) in the treatment of BPD.

D. Resource Sharing Plan

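### C.5.2 corrects R33 clinical outcomes by Holm under Aim R33-1 and by Bonferroni after Aim R33-4, without saying which tests each covers; Holm for both would lose nothing in error control

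*Combined protocol and SAP*

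**What the plan says.** All the relevant text is in C.5.2, with the outcome list in C.3.3.

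- **Primary.** "The primary outcome measure is the Zanarini total score", compared between groups for change from baseline to end of treatment (EOT).
- **Aim R33-1, other outcomes.** The additional measures of C.3.3 get a similar analysis, "using the Holm's procedure for correction for multiple comparisons". C.3.3 lists the ZAN-BPD sector scores (number not given), ALS, PSS, DERS, BDI and a state-trait anxiety score.
- **Aim R33-4.** "Aim R33-4: As above, we will use linear mixed models to examine change in ZTS as the outcome variable".
- **Next sentence.** "Bonferroni corrections will be applied for multiple clinical outcome measures". It names no measures, visits or number of tests.
- **Level.** "P-values throughout will be 0.05, two tailed".

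Sections A.2 and C.2.3 say the clinical measures are reassessed 1 and 4 months after treatment. The wording of Aim R33-4 itself is not in the documents.

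**The concern.** Two multiplicity procedures appear a few lines apart for R33 clinical outcomes, and neither is tied to a defined set of tests. Aim R33-4 names only the Zanarini total (ZTS), so a sentence about several clinical measures must reach beyond the outcome just named. The plan does not say how far.

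Two things are at stake. If the sentences overlap, the plan gives two decision rules for one p-value, and the choice could be made after the results are seen. If they do not overlap, the second family is tested with a procedure that can miss effects Holm would declare and never declares one that Holm would miss.

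**Working it through.** **1. The plan's own figure.** C.7 takes the planning effect from a meta-analysis that "reported an effect size of 0.56 for seven stand-alone trials employing BPD-relevant outcomes". With power 0.80 and two-sided 0.05, n per group = 2 × (1.960 + 0.842)² / 0.56² = 50.1, so 51. The t-based solution is 51.03, and power at 51 is 0.800. The stated 51 per group is reproduced. It is for one primary test and involves no multiplicity correction.

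**2. The two rules.** For m tests, Bonferroni compares every p-value with 0.05/m. Holm orders the p-values and compares the i-th smallest with 0.05/(m − i + 1), stopping at the first failure. C.3.3 gives five named scales plus an unstated number of sector scores. Assuming four sectors, m = 9:

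- Bonferroni: 0.05/9 = 0.0056 for every test.
- Holm: 0.05/9 = 0.0056, then 0.05/8 = 0.0063, 0.05/7 = 0.0071, and so on up to 0.05.

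Holm's thresholds are never below Bonferroni's, so it rejects everything Bonferroni rejects. The first step is the same, so the chance of at least one rejection is identical. Both guarantee familywise error of at most 0.05 under any dependence.

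**3. When the two sentences would disagree.** If the smallest p-value passes and the second smallest lies between 0.0056 and 0.0063, that second outcome is significant under Holm and not under Bonferroni. This matters only if both sentences apply to it.

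**4. Size of the power difference.** Inputs: 51 per arm and d = 0.56 (C.7, where they belong to the primary outcome). Assumed: m = 9, pairwise correlation 0.5, and the effects in each scenario. The mean of each test statistic is 0.56 × √(51/2) = 2.828. As a check, Bonferroni power per outcome is Φ(2.828 − 2.773) = 0.522, which matches the simulation (40,000 replicates, normal statistics):

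| True effects | Average power, Bonferroni | Average power, Holm | Gain | At least one real effect declared (either method) |
|---|---|---|---|---|
| All nine d = 0.56 | 0.523 | 0.634 | 0.111 | 0.913 |
| Four of nine d = 0.56 | 0.521 | 0.548 | 0.027 | 0.817 |
| One of nine d = 0.56 | 0.523 | 0.523 | 0.000 | 0.523 |
| All nine d = 0.3 | 0.105 | 0.127 | 0.022 | 0.399 |

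Simulated familywise error was 0.040 for both methods with no true effects, and 0.024 (Bonferroni) against 0.032 (Holm) with four of nine real.

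**5. Sensitivity to the assumed count.** With all effects at d = 0.56 and correlation 0.5, average power goes from 0.600 to 0.698 at m = 5 and from 0.577 to 0.683 at m = 6.

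**6. Why the family definition matters more.** Adding ZTS to nine measures gives 10 tests. Counting months 1 and 4 separately gives 10 × 2 = 20. The Bonferroni threshold, which is also Holm's first step, moves from 0.0056 to 0.05/10 = 0.0050 to 0.05/20 = 0.0025. The documents do not say which applies.

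**The case against.** The strongest reply is that nothing here is wrong. Holm is tied to Aim R33-1 and Bonferroni follows Aim R33-4, and different aims may use different procedures. Bonferroni is valid, and it gives simple simultaneous confidence intervals that match its tests, which Holm does not.

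Much of this stands. A reader might infer that the plan contradicts itself on the same tests, but the documents do not show that. The Bonferroni sentence may cover follow-up measures. It may be a general rule, since the sentences after it apply throughout. It may also reach the clinical-outcome regressions of C.6.4. The conflict is therefore conditional on an overlap that the text neither states nor rules out.

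It is also fair to object that the nine-outcome illustration borrows the C.3.3 list, for which Holm is already prescribed, and the planning values of the primary outcome. The size of the Bonferroni family and its effects are unknown.

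The confidence-interval argument has little force here, because C.5.2 describes its corrections in terms of p-values and does not call for simultaneous intervals. The reply also leaves the main gap open: neither family can be written down from the text.

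**Conclusion.** The point holds as a minor, nearly free improvement. C.5.2 names two procedures without a reason and without listing the tests. Under the overlapping reading the decision rule is ambiguous. Under the separate-family reading Bonferroni is valid but never more powerful than Holm at the same guaranteed error.

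The gain in average power runs from none to about 11 points across the scenarios shown. A reader might take the 11 points, or the rise from 0.11 to 0.37 in the chance of declaring all nine, as the expected benefit. The documents do not support that: it requires every outcome to be affected at the primary planning effect. A reader might also infer that Holm wins in every case. It is never worse, but it ties when one outcome is affected, and always ties on the chance of at least one rejection.

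Type I error is not inflated, and the EOT test of ZTS and its 51 per group are untouched. The number of sectors, the correlation, the secondary effects and the use of 51 per arm for these families are assumptions.

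**What to change.** Replace the Bonferroni sentence in C.5.2 with Holm, and define two families, each at two-sided 0.05:

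1. The C.3.3 secondary outcomes at EOT, listed by name, with the number of ZAN-BPD sector scores stated.
2. The follow-up clinical outcomes, listing the measures and the visits (1 and 4 months), saying whether the two visits count as separate tests and whether ZTS is included.

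State that the EOT test of ZTS is the single primary test and lies outside both families. If the Bonferroni sentence was meant for something else, such as the C.6.4 regressions, say so and list those tests as their own family.

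The cost is a few sentences, settled before R33 outcome data are analysed. Data collection, sample size and the primary analysis do not change. The one thing given up is the simple simultaneous confidence intervals that match Bonferroni, which the plan does not ask for.
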